18.0 PUBLICATION POLICY	
19.0 TRIAL RECORD RETENTION AND ARCHIVING	42
REFERENCES	43
APPENDICES	
Appendix 1: List of Prohibited Medications	44

[figure not shown]
LIST OF ABBREVIATIONS

AE	Adverse Event
AR	Adverse Reaction
CA	Competent Authority
CI	Chief Investigator
CRF	Case Report Form
CRP	C-Reactive Protein
СТА	Clinical Trial Authorisation
CTIMP	Clinical Trial of Investigational Medicinal Product
СТРМ	Clinical Trial Project Manager
CVD	Cerebral Vascular Disease
EC	European Commission
EU	European Union
GCP	Good Clinical Practice
GMP	Good Manufacturing Practice
IB	Investigator Brochure
ICF	Informed Consent Form
IDMC	Independent Data Monitoring Committee
IMP	Investigational Medicinal Product
IMPD	Investigational Medicinal Product Dossier
ISF	Investigator Site File
ISRCTN	International Standard Randomised Controlled Trial
	Number
MA	Marketing Authorisation
MAHSC – CTU	Manchester Academic Health Science Centre – Clinica
	Trials Unit
MCA	Middle Cerebral Artery
MHRA	Medicines and Healthcare products Regulatory Agency
MRI	Magnetic Resonance Imaging
mRS	Modified Rankin Score
NINCDS-ADRDA	National Institute of Neurological and Communicative
	Disorders and Stroke and the Alzheimer's Disease and
	Related Disorders Association
NHS R&D	National Health Service Research & Development
NIHSS	National Institutes of Health Stroke Scale
PET	Positron Emission Tomography
PI	Principal Investigator
PIS	Participant Information Sheet
QUADAS	Quality Assessment of Diagnostic Accuracy Studies
RCT	Randomised Control Trial
REC	Research Ethics Committee
SAR	Serious Adverse Reaction
SAE	Serious Adverse Event
SDV	Source Document Verification
SmPC	Summary of Product Characteristics
SOP(s)	Standard Operating Procedure(s)

SUSAR	Suspected Unexpected Serious Adverse Reaction
TMG	Trial Management Group
TSC	Trial Steering Committee
TSPO	Translocator protein
VCI	Vascular Cognitive Impairment
WMIC	Wolfson Molecular Imaging Centre

TRIAL SUMMARY

Title:	Imaging cerebral neuroinflammation in acute and chronic cerebrovascular disease: a predictor of outcome and biomarker for guiding treatment.
Design:	Observational, cross-over study, two phase study.
Objectives:	Phase 1 (months 1-12):
	 Evaluating the tolerability of scanning using a questionnaire given to the participants, asking them to grade the discomfort associated with the [¹⁸F]GE-180 procedure on a 5 point scale, the average score must be neutral (score 3) or better. The technical feasibility will be assessed by evaluating the Translocator Protein TSPO on imaging using the [¹⁸F]GE-180 as the radiotracer. In particular, we will examine whether patients with the heterozygote genotype (identified by blood tests but analysed retrospectively), who are expected to present as medium binders, will provide quantifiable scans. A Correlation coefficient of 0.5 or higher between the focal abnormalities observed with the two different tracers in ischemic stroke patients, indicates that measurements are comparable.
	Phase 2 (months 13-39):
	 Examine whether the extent and intensity of microglial activation is related to functional outcome in stroke patients (disability scores, such as the NIHSS and the Modified Rankin Score, relative to initial assessment) Determine the location of microglial activation including infarct border zones and functionally connected brain regions in comparison with structural lesions as delineated on MRI and neurological deficits in patients after stroke Examine whether the intensity of microglial activation is related to systemic inflammation
Endpoints	1) Data acquisition in at least 10 patients and feasibility analysis completed within 12 months.
	2) Data acquisition on 50 patients (shown to not have homozygote genotype) and collection of functional outcome data (as assessed at 3 month follow-up).
	3) Analysis and statistical comparison of MRI/PET scans compared to the functional outcome.
Patient Group:	Ischaemic stroke patients (n=50 excluding patients with homozygote genotype)
Eligibility	Ischaemic stroke in MCA territory (I63.0 to I63.5), mild to moderate severity (Modified Rankin Scale score1-3)

(Recruited from the research hospital sites where initial clinical assessment is carried out and 3 month follow-up; All other procedures will be performed at WMIC and Central Manchester University Hospital NHS Foundation Trust).

1.0 BACKGROUND

Reduced blood supply to the brain causes ischaemia and can result in severe tissue damage. An acute and severe regional blood flow reduction would typically cause a stroke, while a less severe but chronic and widespread reduction may cause impairment of brain function, including an impairment of cognitive processes e.g. memory and action planning. Although the severity and duration of the blood flow impairment is an important factor to predict the severity of symptoms and functionality, basic and clinical research has demonstrated that inflammation also contributes to the outcome.

Inflammation of brain tissue and blood vessels can increase the severity of stroke, and there are also indications that it may increase the severity of cognitive impairment. Microglial cells are an important type of glial cell. These non-neuronal cells have several functions in supporting nerve cells, including regulating immune and inflammatory responses in the brain. Microglia may damage tissue as a result of secreting inflammatory proteins (cytokines), but will also ultimately contribute to the removal of irreversibly damaged brain cells [Ransohoff and Cardona, (2010)]. Activated microglia are also present along neuronal pathways in areas remote from the initial damage, and probably contribute to the impairment of neuronal function and limit recovery in stroke patients [Dirnagl *et al.*, (1999)].

Acute stroke and vascular cognitive impairment (VCI) are part of a spectrum of cerebrovascular disease. In acute cerebral infarcts, the penumbra accumulates an abundance of activated microglia [Ransohoff and Cardona, (2010)]. The presence of microglia-derived brain macrophages is an important contributor to the early and late stages of the tissue pathology and therefore therapeutic strategies aimed at modulating microglial activation are key [Dirnagl *et al.*, (1999)]. Experimental and clinical studies have demonstrated that the neuroinflammatory response contributes to the extent of brain tissue damage and can be primed by systemic inflammation [Okun *et al.* (2011), Emsley *et al.* (2007), Drake *et al* (2011)]. However, neuroinflammation cannot satisfactorily be detected by current clinical brain imaging methods. Using better imaging techniques in anticipation of identifying patients with increased microglial activation, will permit us to more accurately correlate clinical outcomes in practice and in clinical studies using anti-inflammatory drugs [Emsley *et al.* (2005)].

1.1 Rationale for the proposed trial

There are two main objectives for the study; initially to evaluate whether a technique for microglial imaging is feasible and secondly to evaluate whether imaging of microglial activation predicts outcome and clinical progression in patients with stroke.

PET and the radiotracer [¹¹C]-(R)-PK11195 can provide a quantitative assessment of microglial activation in human subjects. [¹¹C]-(R)-PK11195 (1-[2-chlorophenyl]-N-methyl-N-[1-methyl-propyl]-3-isoquinoline carboxamide) is a specific ligand for the mitochondrial 18kDa translocator protein (TSPO), which is particularly abundant in activated microglia. Labelled with carbon-11 (¹¹C), the radiotracer has been used to image activated microglia in several neurological disorders including completed ischaemic stroke [Pappata *et al.* (2000), Garhard *et al.* (2005), Price *et al.* (2006), Thiel *et al.* (2010)]. Clinical and preclinical animal model data suggest that it is a very sensitive tool to monitor the evolution of microglial activation after a stroke demonstrating the early recruitment of microglia in the ischemic border zone and later involvement of the neocortex and thalamus [Myers *et al.* (1991)]. Unfortunately, the physical half-life time of ¹¹C (~20 min) is too short to allow routine clinical use of [¹¹C]-(R)-PK11195. This study however, will measure the extent of the inflammation in patients with stroke using positron emission tomography (PET) and a new radiotracer ([¹⁸F]GE-180) that binds specifically to activated microglia.

In the past few years, a new generation of tracer has been developed [Winkeler *et al.* (2010)]. (S)-N,N-diethyl-9-(2-[18F]fluoroethyl)-5-methoxy-2,3,4,9-tetrahydro-1H-carbazole-4-carboxamide (¹⁸F-GEH120714, [¹⁸F]GE-180) is a novel PET ligand with high affinity (0.87 nM) and selectivity for TSPO. Additionally, it has an *in vivo* performance superior to that of [¹¹C]-(R)-PK11195. Labelling with fluorine-18 (¹⁸F) that has a physical half-life of 110 minutes, makes it much more amenable for routine clinical use. [¹⁸F]GE-180 is being developed by GE Healthcare (patent WO2011117421) as a clinical PET biomarker of microglial activation.

All second-generation tracers provide high-affinity binding with low background, but signal intensity is influenced by a genetic polymorphism (Ala147Thr) that has recently been identified on the TSPO gene [Owen *et al.* (2012)]. For each individual, the genetic polymorphism and the associated binding status can be determined using blood samples.

Previous PET studies of microglial activation in similar, but smaller patient groups using [¹¹C]-(R)-PK11195 have been conducted. In a study of volunteers at high risk for ischaemic stroke, a significant relationship of systemic inflammation, as indicated by increased plasma C-reactive protein (CRP) levels was found [Drake *et al* (2011)]. In another study in patients with mild cognitive impairment and Alzheimer's disease, increased microglial binding was found [Edison *et al.* (2008)]. A recently completed study in patients with gliomas compared to normal controls found an increased signal in malignant tumours and, to a lesser degree but still significant, also in normal brain tissue. Methods for TSPO receptor quantification using supervised reference tissue extraction techniques have been developed and validated [Turkheimer *et al.* (2007)]. Preclinical studies using [¹⁸F]GE-180 in WMIC laboratory demonstrated excellent TSPO binding [Owen *et al.* (2011)]. [¹⁸F]GE-180 uptake was significantly higher in the core of ischaemic lesions (+24%) and lower in the healthy contralateral tissue (-18%) than [¹¹C]-(R)-PK11195 and thus gave a significantly better contrast between the lesion and the healthy tissue. Full displacement of [¹⁸F]GE-180 was obtained within 5-10min post-injection of the cold ligand (Figure 1). Pilot studies in human patients are currently being conducted by GE Healthcare in Canada. These data also indicate that the biological properties of [¹⁸F]GE-180 are similar to 18F-DPA-714, suggesting high specific binding with moderate dependency on receptor activation status [Owen *et al.* (2011)].

[figure not shown]

Figure 1. Accumulation of [¹⁸F]GE-180 and displacement by cold [¹¹C]-(R)-PK11195 in an experimental ischemic infract [Dickens *et al.* (2014)].

By evaluating the relationship of the inflammatory changes with the clinical symptoms and their change (progression or recovery) after 3 months, it will be determined whether neuroinflammation does have an impact on the severity and prognosis of clinical impairment. This will answer the important issue of whether microglial activation is actually associated with more severe symptoms and poor clinical outcome and will potentially open new avenues for effective drug development to target this pathophysiological mechanism. This is highly relevant for treatment since drugs that aim to suppress neuroinflammation are currently being tested, and the study will indicate whether these drugs could also be beneficial to patients with stroke.

2.0 TRIAL OBJECTIVES AND ENDPOINTS

The study aims to evaluate the association between microglial activation and the outcome in stroke patients. The data produced by the study will assess whether neuroinflammation has an impact on the severity and prognosis of clinical impairment in stroke patients. The first year of the trial will assess the technical feasibility, whilst ensuring that the patients can tolerate the

scanning procedures. If phase 1 of the study is successful, the trial will move onto phase 2. During phase 2 of the study, data will be collected on a further 40 patients, ensuring that by the end of the trial there will be data on 50 stroke patients. The data from the entire study will be used to identify the location and quantifying the degree of microglial activation after stroke and determine if a correlation between clinical outcome and inflammation can be demonstrated.

2.1 Phase 1 Objective

The initial objective is to evaluate whether the proposed technique for microglial imaging is feasible. This evaluation will be performed over the first twelve months, (or as soon as the first 10 patients have received both [¹¹C]-(R)-PK11195 and [¹⁸F]GE-180 scans.) and will reviewed by the IDMC. Criteria of feasibility will be assessed by:

A) Evaluate the tolerability of scanning using a questionnaire given to the participants, asking them to grade the discomfort associated with the [¹⁸F]GE-180 procedure on a 5 point scale, the average score from the tolerability questionnaire must be neutral (score 3) or better.

B) Evaluate the technical feasibility of the imaging using the [¹⁸F]GE-180 as the radiotracer. In particular, we will examine whether patients with the heterozygote genotype (as identified by the blood test which will be tested retrospectively), who are expected to present as medium binders, will provide quantifiable scans.

C) A Correlation coefficient of 0.5 or higher between the focal abnormalities observed with the two different tracers in ischemic stroke patients, indicates that measurements are comparable.

Analysis of data from the 3 month follow-up assessments are not necessary for the phase 1 data analysis but will be included in the phase 2 analysis.

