2.3 Endpoints

Phase 1:

- 1) Data acquisition in 10 patients.
- 2) Technical feasibility analysis completed within 12 months. Assessing if it is possible to obtain quantifiable scans from patients with heterozygote genotype and that the frequency of the low-binding genotype (Thr147/Thr147) in this population is rare.
- 3) Tolerability levels recorded for 10 patients. The threshold for tolerability is the average score of neutral (score 3 out of 5) or better, as assessed by the tolerability questionnaire.

Phase 2:

- 1) Data acquisition on 50 patients (replacing the patients that are shown to have a low binders, genotype Thr147/Thr147, as assessed by the blood test)
- 2) Completion and analysis of the clinical assessments (performed 3 months apart) on 50 patients (replacing the patients with a low binders, genotype Thr147/Thr147, as assessed by the blood test).

It is expected that a few patients, even though they might not indicate that at the time of inclusion/consent, will leave the study before undertaking the PET scan. MRI scanning is usually perceived as the most stressful investigation because it involves the patient being scanned in a confined space and it also involves a significant level of noise, compared to PET scanning. Patients leaving the study at this stage before receiving the first PET scan, will be replaced by additional recruits. Patients, who leave the study at a later stage would not be replaced and counted as follow-up failures.

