4.3.2 Early discontinuation of trial

The early stopping rules for efficacy will be based on the phase 1 analysis. Depending on the outcome of this stage, we will either continue without modification, make appropriate modifications or, in case of insurmountable problems or poor tolerability of the scanning protocol will stop the study. This critical 'Go/No-Go' decision will also be based on advice from the trial steering committee, the sponsor and the funder, who will be informed about study progress, the results of the tracer comparison and patient feedback prior to the second milestone meeting. Efficacy will be based on:

- The comparison of the new tracer ([¹⁸F]GE-180) with the already established [¹¹C]-(R)-PK11195 in 10 patients.
- Patient tolerability questionnaire about the feasibility in terms of experience and comfort.
- Technical feasibility of the scans, whether the participants with the heterozygote genotype will provide quantifiable scans.

An Independent Data Monitoring Committee (IDMC) will be appointed who will oversee patient safety and any recommendations from the IDMC (which may include stopping the trial after phase 1) will be considered by the Trial Steering Group. The IDMC will be presented with the

phase 1 data for consideration and a decision whether to continue onto phase 2 will be reached before the end of month 12.

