10.0 TRIAL CLOSURE

All patients will be followed up 3 months (± 2 weeks) after their initial stroke.

The first possible endpoint is at the end of year 1. If the trial does not satisfy the 'Go/NoGo' criteria (defined in section 4) the trial will be closed. All patient data gathered in the first year will be kept by WMIC and used for analysis.

The data acquisition endpoint is at the end of 39 months. Data will have been collected on 50 patients (excluding any low -binding patients as described in previous sections).

The final endpoint of the trial is at the end of 4 years (39 months of data collection plus 9 months of scanning analysis and statistical analysis of the correlation between microglial activation and the functional outcome of the patients). All data collected from phases 1 and 2 will have been analysed.

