11.2 Interim analysis

The interim analysis will be carried out at the end of phase 1. It will be based on the feasibility of obtaining scans on patients who heterozygous for the TSPO rs6971 polymorphism. The analysis will also include information from the tolerability questionnaires that patients will be asked to complete at the end of the 2 day scanning process.

Main objective is to obtain information on:

- Technical feasibility of the [¹⁸F]GE-180 scans and the possibility of reducing the scan time to 20 minutes.
- Use tolerability information gathered from patients about the comfort and duration of the scans.
- Ensure that the correlation between [¹¹C]-(R)-PK11195 and [¹⁸F]GE-180 images has a coefficient correlation of 0.5 or higher.

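### A between-tracer correlation of 0.5 in ten Phase 1 patients is a rough feasibility signal and cannot show that the two tracers' measurements are comparable

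*Protocol*

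**What the plan says.** Section 2.1 gives three feasibility criteria: tolerability (A), technical feasibility with attention to heterozygotes (B), and the tracer comparison (C). Criterion C reads that a correlation "of 0.5 or higher between the focal abnormalities observed with the two different tracers in ischemic stroke patients, indicates that measurements are comparable". The Trial Summary carries the same statement. The evaluation takes place over the first twelve months or "as soon as the first 10 patients have received both" scans.

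Section 11.2 repeats the threshold as an interim objective: the correlation between the two tracers' "images has a coefficient correlation of 0.5 or higher". Neither section attaches a confidence interval, a measure of agreement or a unit of analysis to it.

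Four other places bear on the point:

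- Section 11.3 says the tracers will be compared by correlation on summed images, using target-to-reference ratios. For the older tracer it places the reference region in the contralateral hemisphere.
- Section 1.1 reports preclinical uptake of the new tracer, relative to the older one, of +24% in the lesion core and -18% in healthy contralateral tissue.
- Section 11.1 puts the emphasis on interval estimation. It plans Phase 2 on a one-sided 90% lower limit of 0.200 for a correlation of 0.400 with 37 patients.
- Section 2.3, Phase 1 item 2, includes assessing that "the frequency of the low-binding genotype (Thr147/Thr147) in this population is rare". It sets no figure for rare.

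**The concern.** Criterion C does two things at once. It sets a threshold, and it says what reaching the threshold means. The threshold is a usable screening value. The stated meaning is the fault, for two reasons.

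First, comparability of two measurements is a question of agreement, and r does not measure agreement. Two tracers can correlate well while giving systematically different values.

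Second, the rule rests on a point estimate from ten patients, although the protocol elsewhere asks for intervals.

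At stake is what can be said after Phase 1. A result just over the line would, on the protocol's wording, entitle the team to report that the new tracer's measurements are comparable with those of the established one. The data would be compatible with anything from no association to a strong one, and would not have addressed agreement.

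The genotype item has the same weakness on a smaller scale: a statement about frequency that ten patients cannot support.

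**Working it through.** **Inputs.** n = 10 with both tracers (sections 2.1, 2.3 and 4.3.2); threshold r = 0.5 (sections 2.1 and 11.2); preclinical differences of +24% and -18% (section 1.1); Phase 2 planning figure n = 37, r = 0.40, one-sided 90% limit 0.200 (section 11.1). Assumptions: one value per patient and bivariate normality. Section 11.1 makes the latter assumption for Phase 2.

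**Step 1: reproduce the protocol's own figure.** The Fisher z lower limit is tanh(atanh(r) - z/sqrt(n - 3)). With r = 0.40, n = 37 and z = 1.2816: tanh(0.4236 - 1.2816/sqrt(34)) = tanh(0.2038) = 0.201. The n that gives exactly 0.20 is 36.65, so 37. The section 11.1 figure is correct.

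**Step 2: apply the same formula to Phase 1.** With r = 0.5 and n = 10, atanh(0.5) = 0.5493 and sqrt(7) = 2.6458.

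- Two-sided 95%: tanh(0.5493 ± 1.96/2.6458) = tanh(-0.1915) to tanh(1.2901) = -0.19 to 0.86.
- One-sided 90%, the form used in section 11.1: tanh(0.5493 - 0.4844) = 0.06.
- For the one-sided 90% limit to reach 0.20 with 10 patients, the observed r would have to be about 0.60. For it to reach 0.5, r would have to be about 0.78.
- If only 8 of the 10 pairs were usable, the 95% interval at r = 0.5 would be -0.32 to 0.89 and the one-sided 90% limit -0.02.

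**Step 3: how often the rule is met.** For true correlation 0, the exact test gives t = 0.5 × sqrt(8/0.75) = 1.633 on 8 df, one-sided probability 0.071. The other rows come from simulating 400,000 bivariate normal samples of 10.

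| True correlation | Chance that r is 0.5 or more |
|---|---|
| 0 | 7% |
| 0.3 | 27% |
| 0.5 | 54% |
| 0.7 | 84% |
| 0.8 | 95% |

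**Step 4: what r = 0.5 says about agreement.** Shared variance is 0.5² = 25%. For any constant a > 0, the correlation of aX with Y equals that of X with Y, so r cannot detect a scale difference. If the preclinical differences carried over to patients (an assumption), the new tracer's lesion-to-contralateral ratio would be 1.24/0.82 = 1.51 times the older tracer's. A constant factor of that size leaves r exactly where it was.

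**Step 5: the genotype item.** With 0 of 10 low binders, the exact two-sided 95% upper limit is 1 - 0.025^(1/10) = 30.8%. With 1 of 10, the interval is 0.3% to 44.5%. If the true frequency were 10% (an assumed value; the protocol gives none), 0 of 10 would occur with probability 0.9^10 = 35%.

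**The case against.** The strongest defence is that this is a feasibility screen in a self-described feasibility study, and as a screen it discriminates reasonably: it passes 7% of the time when there is no association and 95% when the association is 0.8. The 54% at a true value of 0.5 is roughly what any cut-off gives when the truth lies on it. This stands, and it is why the threshold itself can stay. A reader might infer that the decision is largely a matter of chance; the pass rates do not support that.

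The two-sided 95% interval is also not the protocol's chosen standard for correlations. On the one-sided 90% form in section 11.1 the lower limit is above zero. That is true, but 0.06 is weak, and well short of the 0.20 used to plan Phase 2.

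Agreement, it can be said, is not needed for the trial's purpose. Phase 2 uses the new tracer alone and relates it to outcome by correlation and regression, so a constant scale factor does no harm. Section 1.1 presents the expected difference as an advantage. This stands for the Phase 2 analysis. It does not rescue the wording, because it argues for a statement about association and criterion C makes one about comparability.

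On the genotype item, section 2.3 lists something to be assessed, with no pass limit, and it is not among the bases for the decision in sections 4.3.2 or 11.2. That stands, so the item is a wording point only.

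**Conclusion.** The conclusion attached to criterion C is wrong as written and should be fixed. A correlation of 0.5 or more in 10 patients supports a cautious statement that the two tracers are associated. It does not show comparable measurements: the 95% interval at the threshold runs from -0.19 to 0.86, and no value of r would address agreement. The figures assume one value per patient and bivariate normality; the 1.5-fold example also assumes that the preclinical differences carry over to patients.

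Four stronger readings are not supported:

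- *Criterion C is the sole gate to Phase 2, or is offered as proof.* Sections 2.1 and 4.3.2 name tolerability and technical feasibility as well, and add advice from the steering committee, sponsor and funder and review by the data monitoring committee. The protocol's verb is weaker than proof.
- *Mixing genotypes will depress r.* The protocol does not say how genotype enters the Phase 1 correlation. That may be settled in an analysis plan, and the size of any effect would rest on a shift the protocol does not give.
- *Pooling regions will inflate r.* The protocol does not say that regions are the data points, and the size would depend on an assumed spread between regions.
- *Sections 4.3.2 and 10 conflict on whether failure is binding.* Section 10 closes the trial if it does not meet the "criteria (defined in section 4) the trial will be closed". That can be read as importing the rule in section 4.3.2, under which "we will either continue without modification, make appropriate modifications or, in case of insurmountable problems" or poor tolerability, the study stops.

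**What to change.** In the Trial Summary and section 2.1, keep 0.5 as a minimum feasibility signal. Replace the clause about comparability with a statement that the two tracers' focal findings are associated. In sections 2.1 and 11.2, state that r is computed from one prespecified lesion-to-reference value per patient and reported with its confidence interval.

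Before any statement that the tracers are comparable, describe agreement on the paired ratios, for example with a Bland-Altman plot. A log scale would suit, because a proportional difference is expected. With ten pairs this is descriptive only.

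In section 2.3, drop the wording that the genotype is rare. Report the low-binder frequency with an exact confidence interval at the end of the trial. The denominator must be all genotyped patients, because low binders are replaced and are therefore absent from the final 50 by design. For scale, 0 of 50 genotyped would have an exact two-sided 95% upper limit of 7.1%, against 30.8% for 0 of 10.

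The cost is a wording amendment and a few analyses of data already being collected, with no extra patients or scans. The downside is a weaker statement about the two tracers after Phase 1.
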